7.2.5 Reasons for discontinuation

The reasons for discontinuation from participation in the registry will be collected and classified as:

- Death
 - For patients who discontinue due to death, then 'Death' will be recorded as reason for discontinuation. Patient's date of death, cause of death and phase of disease during which death occurred will be recorded, as permitted by local regulations.
- Lost to follow up
 - Patients lost to follow up should be recorded as such on the CRF. For patients who are lost to follow-up, the treating physician and/ or designee should show "due diligence" by documenting in the source documents steps taken to contact the patient, e.g. dates of telephone calls, registered letters, etc.
- Subject withdrew consent
- Administrative problems
- Treatment duration completed / condition no longer requires treatment
- Protocol deviation

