7.7.4.2 Main secondary endpoints

The main secondary efficacy endpoint will be overall survival (OS).

OS is defined as the time from diagnosis to death from any cause.

Censoring date will be the date of last contact for patients who are still alive.

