7.7.5.2 Adverse events (AEs)

The incidence of - adverse events (new or worsening from baseline) will be summarized by system organ class and or preferred term, severity (based on CTCAE grades), type of adverse event, relation to study treatment.

Deaths reportable as SAEs and non-fatal serious adverse events will be listed by patient and tabulated by type of adverse event.

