9.1 Adverse event definitions and reporting

An adverse event (AE) is defined as the appearance of (or worsening of any pre-existing) undesirable sign(s), symptom(s), or medical condition(s) in a patient administered imatinib (Glivec[®]) that does not necessarily have a causal relationship with the treatment.

An AE can therefore be any unfavorable and unintended sign (including an abnormal laboratory finding), symptom, or disease temporally associated with the use of imatinib (Glivec[®]), whether or not related to the medicinal product(s).

Abnormal laboratory values or test results constitute adverse events only if they induce clinical signs or symptoms, are considered clinically significant, require therapy or require changes in medication(s) dose.

Adverse events that begin or worsen during imatinib (Glivec[®]) administration should be recorded in the Adverse Events CRF. Conditions that were already present at the time of diagnosis and until the first dose of imatinib (Glivec[®]) should be recorded in the Medical History page of the patient's CRF. Adverse event monitoring should be continued for at least 30 days (or 5 half-lives, whichever is longer) following the last dose of treatment. Adverse events (including lab abnormalities that constitute AEs) should be described using a diagnosis whenever possible, rather than individual underlying signs and symptoms. When a clear diagnosis cannot be identified, each sign or symptom should be reported as a separate Adverse Event.

Adverse events will be assessed according to the Common Terminology Criteria for Adverse Events (CTCAE).

The occurrence of adverse events should be sought by non-directive questioning of the patient at each visit during the study. Adverse events also may be detected when they are volunteered by the patient during or between visits or through physical examination, laboratory test, or other assessments. As far as possible, all adverse events should be recorded on the Adverse Events case report/case record form (CRF) with the following information:

- 1. the severity grade (CTCAE Grade 1-4)
- 2. its relationship to the drug(s) of interest (suspected/not suspected)
- 3. its duration (start and end dates or if continuing at final exam)
- 4. action taken with respect to imatinib (Glivec[®]) treatment during registry period (no action taken, dose adjusted/ temporarily interrupted, permanently discontinued, unknown, not applicable)

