- 5. whether medication or therapy was given (concomitant medication taken, non-drug therapy given)
- 6. whether it constitutes a serious adverse event (SAE) as defined in Section 9.3.

In addition, all reports of the following special scenarios are also considered an adverse event irrespective if a clinical event has occurred:

- Drug-drug or drug-food interaction
- Drug exposure during pregnancy
- Drug use during lactation or breast-feeding,
- Lack of effectiveness
- Overdose
- Intentional drug abuse and misuse
- Medication error including drug maladministration
- Dispensing or prescribing errors
- Drug dependence or addiction
- Unexpected beneficial effect
- Off-label use
- Withdrawal or rebound symptoms
- Treatment non-compliance (with clinical symptoms)

Note: Occupational or accidental exposure, for example of study personnel or family members of the patient should be reported to the local Health Authority in accordance with national regulatory requirements for individual case safety reporting or Novartis CMO&PS as a spontaneous report.

All adverse events should be treated appropriately. Any treatment of any adverse event (e.g. concomitant medication or non-drug therapy) should be recorded on the Adverse Event CRF. Some examples of treatment to be recorded are: no action taken (i.e., further observation only); drug of interest dosage adjusted/temporarily interrupted; drug of interest permanently discontinued due to this adverse event; treatment medication introduced or adjusted; non-drug therapy given; patient hospitalized/patient's hospitalization prolonged.

Once an adverse event is detected, it should be followed until its resolution or until it is judged to be permanent, and assessment should be made at each visit (or more frequently, if necessary) of any changes in severity, the suspected relationship to the study treatment, the interventions required to treat it, and the outcome.

Progression of malignancy (including fatal outcomes), if documented by use of appropriate method, should not be reported as a serious adverse event.

Adverse events separate from the progression of malignancy will be reported as per usual guidelines used for such events with proper attribution regarding relatedness to the drug.

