9.3 Serious adverse event definitions and reporting

Serious adverse event (SAE) is defined as one of the following:

- Is fatal or life-threatening
- Results in persistent or significant disability/incapacity
- Constitutes a congenital anomaly/birth defect
- Requires inpatient hospitalization or prolongation of existing hospitalization, unless hospitalization is for:
 - Routine treatment or monitoring of the studied indication, not associated with any deterioration in condition
 - Elective or pre-planned treatment for a pre-existing condition that is unrelated to the indication under study and has not worsened since the start of the drug of interest
 - Social reasons and respite care in the absence of any deterioration in the patient's general condition
- Is medically significant, i.e., defined as an event that jeopardizes the patient or may require medical or surgical intervention to prevent one of the outcomes listed above e.g. may require treatment on an emergency outpatient basis for an event not fulfilling any of the definitions of a SAE given above and not resulting in hospital admission
- Transmission of infectious agent via medicinal product

In addition, as a Risk Management Plan (RMP) exists for imatinib (Glivec[®]) any events of special interest must be sent to Novartis CMO&PS within the same timelines as a serious adverse event in order to facilitate required follow-up.

To ensure patient safety, every SAE, regardless of causality assessment, occurring after the patient has provided informed consent and until 30 days after the patient has stopped study treatment must be reported to Novartis within 24 hours of learning of its occurrence.

Any SAEs experienced after this 30 days period should only be reported to Novartis if the investigator suspects a causal relationship to treatment with imatinib (Glivec[®]). Recurrent episodes, complications, or progression of the initial SAE must be reported as follow-up to the original episode, regardless of when the event occurs. This report must be submitted within 24 hours of the treating physician or other involved health care professional receiving the follow-up information. An SAE that is considered completely unrelated to a previously reported one should be reported separately as a new event.

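### Section 7.7.5.2 limits the safety death listing to SAE-reportable deaths: it omits progression deaths, may omit late and pre-consent deaths, and is not reconciled with overall survival

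*Protocol*

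**What the plan says.** The safety analyses in section 7.7.5 contain one output on deaths, in 7.7.5.2: "Deaths reportable as SAEs and non-fatal serious adverse events will be listed by patient and tabulated by type of adverse event". The protocol does not define what makes a death reportable there. Three other provisions bear on it.

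- Section 9.1: "Progression of malignancy (including fatal outcomes), if documented by use of appropriate method, should not be reported as a serious adverse event".
- Section 9.3: every SAE "occurring after the patient has provided informed consent and until 30 days after the patient has stopped study treatment must be reported to Novartis". The deadline is 24 hours. For later events the rule is narrower: "Any SAEs experienced after this 30 days period should only be reported to Novartis if the investigator suspects a causal relationship to treatment". The treatment meant is imatinib.
- Section 9.1, first item on the adverse event form: "the severity grade (CTCAE Grade 1-4").

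The efficacy side counts every death. Section 7.7.4.2 states: "OS is defined as the time from diagnosis to death from any cause". Cause is also collected. For patients who discontinue because of death, 7.2.5 states: "Patient's date of death, cause of death and phase of disease during which death occurred will be recorded", as far as local regulations allow. Section 7.3.1.2 adds date and major cause to the OS information.

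**The concern.** This is a post-authorisation safety study imposed because the earlier safety database was small. Its patients receive imatinib with chemotherapy, many of them with transplant, and are followed for at least 5 years from the start of imatinib. A reader of the safety results will want to know how many children died, how many of those deaths came without relapse, and when.

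A rule written for expedited reporting to a sponsor answers a different question. It is built around consent, a 30-day window and suspected causality. If it also sets the scope of the death table, a transplant or infection death in year 3, after imatinib has stopped and with imatinib not suspected, may appear in the OS curve but not in the safety results. The report would then give two death counts with nothing to link them.

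**Working it through.** The plan states no figure to reproduce: the registry is descriptive and has no formal sample size calculation. The check is mainly textual.

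**Step 1. Two readings of reportable.** Reading A is the rule in 9.3 for notifying the sponsor. Reading B is whatever the registry database should hold as an SAE under 7.3.1.8 (collection from the start of imatinib, regardless of relatedness), the opening of section 9 (all events, whatever their cause), 9.1 (30 days after the last dose is a minimum) and Table 7-1 (events marked at post-treatment follow-up and at study completion).

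| Type of death | In OS | Reading A | Reading B |
|---|---|---|---|
| Documented progression | yes | no (9.1) | no (9.1) |
| Other cause, after consent, up to 30 days after last imatinib dose | yes | yes | yes |
| Other cause, later, imatinib suspected | yes | yes | yes |
| Other cause, later, imatinib not suspected | yes | no (9.3) | yes, if the site is still recording |
| Other cause, after start of imatinib but before consent | yes | no (9.3) | yes |

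The first row is excluded on both readings. The last two rows depend on the reading. The last row is not hypothetical: 7.2.1 and 7.2.2 allow patients who died before the registry opened to be included, in order to limit selection bias, and 7.1.1 makes follow-up independent of the enrolment date.

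**Step 2. Can the two counts be reconciled?** OS is analysed in the Full Analysis Set, which requires at least one dose of imatinib with chemotherapy. The Safety set requires at least one dose of imatinib and a valid post-baseline assessment, and 7.7.1 counts a death as one. Every patient who dies in the Full Analysis Set is therefore also in the Safety set, so an all-deaths table in the Safety set should account for every OS death. It also follows that a patient can enter the Safety set because of a death that the death table then leaves out.

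**Step 3. Fatal events in the severity table.** Section 7.7.5.2 tabulates severity by CTCAE grade, while the form item in 9.1 stops at Grade 4. Later in 9.1 the outcome of each event is to be assessed, but 7.7.5.2 plans no summary by outcome.

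**Step 4. Scale, for illustration only.** Inputs: 50 patients (7.5) and OS of 83.6% at 48 months in the continuous-imatinib cohort of the earlier pivotal study (5.3.1).

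- Deaths by 48 months: 50 × (1 − 0.836) = 8.2.
- OS at 60 months, assuming a constant hazard: 0.836^(60/48) = 0.799. Deaths by 60 months: 50 × (1 − 0.799) = 10.0.
- If a share f of those 10.0 deaths were left out, the table would hold 10.0 × (1 − f): 7.5 for f = 25%, 5.0 for 50%, 2.5 for 75% and 1.0 for 90%.

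The documents give no value for f, nor for its parts (progression, late and unsuspected, pre-consent). The range shows how far the two counts could differ; it is not an estimate.

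**The case against.** The strongest case against is that only the loss of progression deaths is certain. Section 7.7.5.2 describes an analysis of registry data, and the collection rules for that database run from the start of imatinib, whatever the causality, and past the end of treatment. On that reading a late transplant death or a pre-consent death is present as a fatal SAE. A separate analysis plan, not shown, could also hold a table of all deaths.

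The first part stands in so far as nobody can say that late and pre-consent deaths are definitely removed. It does not clear the text: the word is undefined, the two readings give different tables from the same data, and neither restores progression deaths. The second part carries less weight, because the protocol does not leave the scope open. It sets it, and sets it narrowly.

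A reader might infer several stronger things that the documents do not support.

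- *That treatment-related mortality will appear too low.* Omitting progression deaths does not lower it, and those deaths are counted in OS. Any understatement can come only from the late and pre-consent deaths, whose loss depends on the reading.
- *That a fatal adverse event cannot be told from a Grade 4 event.* Section 9.1 asks for the outcome, fatality is an SAE criterion in 9.3, and 7.7.5.2 itself separates deaths from non-fatal SAEs. What remains is a mismatch over the grade scale.
- *That the table will show only some stated fraction of the deaths.* Any such fraction rests on assumed shares.

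**Conclusion.** The point holds as a badly fixed scope, and it should be corrected. Section 7.7.5.2 confines the safety death output to a subset of the OS deaths. Documented progression deaths are out on any reading. Late unsuspected deaths and pre-consent deaths are out if 9.3 governs the word reportable, which is the natural reading but not the only one. Deaths without relapse could then be under-shown over an observation period of at least 5 years.

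The direction is certain, since the table cannot hold more than all deaths. The size cannot be derived. The roughly 8 deaths by 48 months and 10 by 60 months in 50 patients assume that the earlier study's survival applies here and, for 60 months, a constant hazard. No deaths are lost to the study as a whole: they enter OS, and cause of death is collected.

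**What to change.** In 7.7.5.2, replace the restriction to SAE-reportable deaths with all deaths in the Safety set, and:

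- list and tabulate them by the cause and disease phase recorded under 7.2.5, with relapse or progression separated from other causes; for deaths seen only at survival follow-up, use the date and major cause in 7.3.1.2;
- split them by timing: up to 30 days after the last imatinib dose or later, and before or after consent;
- flag the SAE-reportable subset and state which rule defines it, the one in 9.3 or the collection rule in 7.3.1.8;
- reconcile the total with the OS deaths in the Full Analysis Set.

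Also reconcile the Grade 1-4 severity item in 9.1 with the CTCAE-grade summary in 7.7.5.2, so that fatal adverse events are shown separately, using the outcome that 9.1 already asks to be assessed.

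The cost is a change of wording in 7.7.5.2, one extra table and an aligned grade or outcome code. The data on deaths are already due to be collected, within the limits of local regulations.

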7.7.5.3 Laboratory abnormalities

Novartis will not have access to individual laboratory values. Clinically relevant laboratory abnormalities will be captured as AEs. There is then no intent to perform specific lab values analyses.

7.7.5.4 Other safety data

Other clinically relevant abnormal safety data collected (e.g. vital signs) will be captured as AEs. No specific analyses will be performed.

7.8 Quality control

Queries related to the completeness and accuracy of the data entered will ensure data quality and integrity. The web-based system will have automatic validation programs to check for data discrepancies in the eCRFs and, allow modification or verification of the entered data by the registry site staff.

7.8.1 Data quality assurance

Novartis Data Management and/ or designee will assure database quality by reviewing the data entered into the eCRFs by investigational staff for completeness and accuracy, and in accordance with the Data Handling Plan.

7.8.2 Data recording and document retention

Each participating site will maintain appropriate medical and research records for this registry, in compliance with standard practice, regulatory and institutional requirements for the protection of confidentiality of subjects. As part of participating in a Novartis-sponsored registry, each site will permit authorized representatives of the sponsor(s) and regulatory agencies to examine (and when required by applicable law, to copy) clinical records for the purposes of quality assurance reviews, audits and evaluation of the study safety and progress.

Source data are all information, original records of clinical findings, observations, or other activities in a clinical trial necessary for the reconstruction and evaluation of the trial. Examples of these original documents and data records include, but are not limited to, hospital records, clinical and office charts, laboratory notes, memoranda, subjects' diaries or evaluation checklists, pharmacy dispensing records, recorded data from automated instruments, copies or transcriptions certified after verification as being accurate and complete, microfiches, photographic negatives, microfilm or magnetic media, x-rays, and subject files and records kept at the pharmacy, at the laboratories, and medico-technical departments involved in the clinical trial.

Data collection is the responsibility of the registry staff at the site under the supervision of the site Principal Investigator. The study case report form (eCRF) is the primary data collection instrument for the study. The investigator should ensure the accuracy, completeness, legibility, and timeliness of the data reported in the eCRFs and all other required reports. Data reported on the eCRF, that are derived from source documents, should be consistent with the source documents or the discrepancies should be explained. All data requested on the eCRF must be recorded. Any missing data must be explained. Any change or correction to a paper eCRF should be dated, initialed, and explained (if necessary) and should not obscure the original entry. For electronic CRFs an audit trail will be maintained by the system.

The investigator/institution should maintain the trial documents as specified in Essential Documents for the Conduct of a Clinical Trial (ICH E6 Section 8) and as required by applicable regulations and/or guidelines. The investigator/institution should take measures to prevent accidental or premature destruction of these documents.

Essential documents (written and electronic) should be retained for a period of not less than fifteen (15) years from the completion of the Registry unless Sponsor provides written permission to dispose of them or, requires their retention for an additional period of time because of applicable laws, regulations and/or guidelines

7.8.3 Site monitoring

Formal site monitoring will be performed as described in the Monitoring Plan for this study.

Before study initiation, at a site initiation visit or at an investigator's meeting, Novartis personnel (or designated CRO) will review the protocol and eCRFs with the investigators and their staff. During the study, the field monitor will visit the site regularly to check the completeness of patient records, the accuracy of entries on the eCRFs, the adherence to the protocol to Good Clinical Practice, the progress of enrollment, and to ensure that study treatment is being stored, dispensed, and accounted for according to specifications. Key study personnel must be available to assist the field monitor during these visits.

The investigator must maintain source documents for each patient in the study, consisting of case and visit notes (hospital or clinic medical records) containing demographic and medical information, laboratory data, electrocardiograms, and the results of any other tests or assessments. All information recorded on eCRFs must be traceable to source documents in the patient's file. The investigator must also keep the original signed informed consent form (a signed copy is given to the patient).

The investigator must give the monitor access to all relevant source documents to confirm their consistency with the CRF entries. Novartis monitoring standards require full verification for the presence of informed consent, adherence to the inclusion/ exclusion criteria and documentation of SAEs. Additional checks of the consistency of the source data with the CRFs are performed according to the study-specific monitoring plan.

7.9 Limitations of the research methods

The research method outlined in this protocol serves as a compromise between a populationbased registry assessing the entirely of the pediatric patient population treated with imatinib in this indication, and an interventional, clinical trial, which would not reflect the breadth of the standard clinical setting.

A non-interventional, observational study design is implicitly associated with known limitations, including difficulty to control external variables and the availability/ completeness of data. In an effort to mitigate these potential limitations, this protocol is well-aligned with the current treatment paradigm and indicates precise data collection requirements to successfully respond to the stated objectives.

In an effort for the registry population to be as representative as possible of the patient population as a whole, no exclusion criteria have been defined. Furthermore, any standard concomitant chemotherapy regimen is permissible. Although this enhances the relevance of the study, it does create a source of non-homogeneity with respect to adverse events related to concurrent chemotherapy. Reasons for non-inclusion will also be identified to permit a possible analysis of any potential bias.

It is recognized that the study is single arm (imatinib + chemotherapy) and lacking a contemporary, external control. Given that current standard medical practice recommends the use of TKIs in the treatment of Ph+ ALL in children, it has previously been acknowledged

that the introduction of such a control would be unfeasible and possibly unethical. Nevertheless, this limitation is recognized by the study team.

